5.3 Patient Transfer and Withdrawal

In consenting to the trial, patients are consenting to trial treatment, follow-up and data collection. If voluntary withdrawal occurs, the patient (or parent/legal representative) should be asked to allow continuation of scheduled evaluations, complete an end-of-study evaluation, and be given appropriate care under medical supervision until the symptoms of any adverse event resolve or the subject's condition becomes stable.

Follow-up of these patients will be continued through the trial Research Practitioners, the lead investigator at each Centre and, where these are unsuccessful, through the child's GP.

5.3.1 Patient Transfers

For patients moving from the area, every effort should be made for the patient to be followed-up at another participating trial Centre and for this trial centre to take over responsibility for the patient or for follow-up via GP.

A copy of the patient CRFs should be provided for the new Centre and its investigator. The patient (or parent/legal representative) will have to sign a new consent form at the new site, and until this occurs, the patient remains the responsibility of the original centre. The CTU should be notified in writing of patient transfers.

5.3.2 Withdrawal from Trial Intervention

Patients may be withdrawn from treatment for any of the following reasons:

- a. Parent/ legal representative (or, where applicable, the patient) withdraws consent for treatment.
- b. Unacceptable adverse effects.
- c. Intercurrent illness preventing further treatment.
- d. Development of serious disease preventing further treatment.
- e. Any change in the patient's condition that justifies the discontinuation of treatment in the clinician's opinion.

If a patient wishes to withdraw from trial treatment, centres should document the reason and explain the importance of remaining on trial follow-up and, if willing, to still have data collected as per trial schedule (actigraphy, sleep and seizure dairies, questionnaires etc), or failing this, to attend clinic and allow routine follow-up data to be used for trial purposes. Generally, follow-up will continue unless the patient explicitly also withdraws consent for follow-up (see section 5.3.3). Following withdrawal from trial treatment patients will be treated according to usual local clinical practice.

5.3.3 Withdrawal from Trial Completely

Patients are free to withdraw consent at any time without providing a reason. Patients who wish to withdraw consent for the trial will have anonymised data collected up to the point of that withdrawal of consent included in the analyses. The patient will not contribute further data to the study and the MCRN should be informed in writing by the responsible physician and a withdrawal CRF should be completed. Data up to the time of withdrawal will be included in the analyses unless the patient explicitly states that this is not their wish.

6 ENROLMENT AND RANDOMISATION

6.1 Screening

A log of potential patients will be kept, including individuals who decide not to participate in the study prior to the T-4W clinic visit and inappropriate referrals from community Paediatricians.

Screening will be performed of a patient's possible eligibility for the study and must be documented on the eCRF at the T-4W clinic visit.

Screening at T-4W (See section 8 for T-4W assessments)

1. Fully informed written proxy consent (and assent, where appropriate) to participate in sleep hygiene intervention.
2. Developmental delay indicated and tested by referrer
3. Documentation of attendance at a special school where applicable
4. ABAS questionnaire score with a percentile rank below 7
5. Documentation of previous/current history of melatonin use
6. History of sleep problems (as described in section 5.1)
7. Pregnancy test for sexually active pubertal females who have consented to this procedure.
8. Electronic submission of T-4W eCRF to MCRN CTU within 24 hours of registration.
9. Forward copy of consent/assent forms to MCRN CTU within 7 days of registration.

6.2 Enrolment/ Baseline

Screening at T0W (See section 8 for T0W assessments)

1. A check of compliance with sleep diary and actigraphy; a minimum of 5 out of every 7 days completed
2. Review of severity of sleep problems (as described in section 5.1)
3. A check that they have not been prescribed melatonin since screening
4. Verification that eligibility criteria continue to be fulfilled.

Randomisation Process:

1. Fully informed written proxy consent (and assent, where appropriate)
2. Completion of randomisation eCRF and trial prescription
3. Attend local pharmacy department (see Table 1 for pharmacy contact details)
4. Randomisation and issue of allocated treatment by pharmacy department
5. See section 8 for T0W assessments
6. Electronic submission of T0W eCRF and allocation notification to MCRN CTU within 24 hours of randomisation by the RP
7. Forward copy of consent/assent forms to MCRN CTU within 7 days of randomisation.

Table 1. Pharmacy Contact Details

If any queries about randomisation procedure contact: Trial Co-ordinator, [name] / [contact] Email: [contact]	
Evelina Children's Hospital, London [name], Pharmacy Department, Evelina Children's Hospital, [name]. [contact] [contact] Email: [contact]	Royal Manchester Children's Hospital [name] Royal Manchester Children's Hospital Central Manchester Foundation Trust Clinical Trials Room 4th Floor In-Patient Pharmacy Dept [name] [contact] [contact] Email: [contact]
Alder Hey Hospital [name] Pharmacy Department Alder Hey Children's NHS Foundation Trust (Alder Hey) [name] [contact] [contact] Email: [contact]	Derbyshire Children's Hospital [name] Derbyshire Hospitals NHS Foundation Trust [name] [contact] [contact] Email: [contact]
University College London Hospitals [name] Pharmacy Department University College Hospital [name] [contact] [name] [contact] Email: [contact]	Nottingham City Hospital [name] Nottingham University Hospitals NHS Trust Nottingham City Hospital Campus [name] [contact] [contact] Email: [contact]
John Radcliffe Hospital [name] Pharmacy dept, Level 2 John Radcliffe Hospital [name] [contact] [contact] Email: [contact]	Southmead Hospital, Bristol [name] Pharmacy Department Southmead Hospital, [name] [contact] [contact] Email: [contact]

7 TRIAL TREATMENT/S

7.1 Introduction

This study is designed as a randomised, controlled, double-blind, multicentre clinical trial comparing the effects of melatonin versus placebo in children with neuro-developmental disorders and impaired sleep. Patients will be treated for a period of 12 weeks and will be followed up throughout this 12 week period.

Patient assessment will be stopped when all patients reach 12 weeks of treatment and/or follow-up.

Patients will be stratified by centre and randomised equally between the two groups:

1. Melatonin
2. Placebo

7.2 Formulation, Packaging, Labelling, Storage and Stability

Melatonin has been sourced by Alliance Pharmaceuticals from a UK fine chemicals manufacturer (SAFC). Manufacture is via a synthetic process to GMP standards.

The proposed formulations will consist of size 2 white opaque capsules at the following strengths:

- 0.5mg
- 2mg
- 6mg
- 12mg

Description and Composition of the Drug Product

Product name: melatonin

Form: oral capsules

Melatonin oral capsules formulation

Melatonin oral capsules, containing melatonin, lactose, and magnesium stearate in a size 2 white opaque, gelatine capsule. The fill weight of each capsule is 200mg. The gelatine is of animal origin.

Capsule contents

Product	Melatonin		Lactose DC		Magnesium stearate		Fill weight
	Active		Diluent		Lubricant		
	%	mg	%	mg	%	mg	
0.5mg	0.25	0.5	99.25	198.5	0.5	1.0	200mg
2.0mg	1.0	2.0	98.5	197.0	0.5	1.0	200mg
6.0mg	3.0	6.0	96.5	193.0	0.5	1.0	200mg
12.0mg	6.0	12.0	93.5	187.0	0.5	1.0	200mg
Placebo	n/a		99.5	199.0	0.5	1.0	200mg

Type of container and closure system:

PVC/PVDC blister with aluminium foil top and outer labelled wallet (labels will include study acronym, EudraCT reference number, randomisation number, visit number, site number, instructions for use and storage, lot number and expiry date)

Stability and shelf life

A batch of 0.5mg and 12mg melatonin oral capsules has been put on an ongoing stability programme. Other than storage at temperatures of less than 25°C, no other special storage precautions would be required for this product.

7.3 Ordering of Trial Supplies

Clinical trial supplies can only be delivered to investigator sites once the site has been initiated. This can only be completed once full ethics and regulatory approval has been granted. This must be confirmed by the Trial Co-ordinator acting on behalf of the study sponsor.

Clinical trial supplies should be requested from Penn Pharmaceutical Services Ltd using the MENDS shipment request form (Appendix G). The size of the first shipment to each site will be pre-determined based on the number of patient packs manufactured for the individual site. The first shipment will be approximately half of the total trial supplies for the site. Once trial supplies are running low (e.g. 3 patient packs remaining) an investigator site may place a second order for the remaining quantity of trial supplies. Each site will have a maximum of two deliveries during the study.

The first section of the MENDS shipment request form should be completed – Investigator Site – Request Details. The form should then be faxed to:

[name], Penn Pharmaceutical Services
[name]

Supplies will then be delivered to the nominated pharmacist at the investigator site within three to five working days.

7.4 Preparation, Dosage and Administration of Study Treatment/s

7.4.1 Dispensing

For each patient treatment will continue for a maximum period of 12 weeks. Upon randomisation patients will be allocated a treatment pack, which will be retained in the pharmacy department and dispensed as detailed below (see also Fig 2 and Appendix I). Each individual treatment pack will comprise:

- 0.5mg – 12 blister packs, each providing 7 days treatment
- 2mg – 11 blister packs, each providing 7 days treatment
- 6mg – 10 blister packs, each providing 7 days treatment
- 12mg – 9 blister packs, each providing 7 days treatment

When pharmacy dispenses the trial treatments they will add their own local dispensing label, which will include the name and address of the hospital, the patient's name, the date of dispensing and instructions for use.

During the 4-week dose increasing phase, trial treatments will be dispensed in volumes sufficient to provide 14 days treatment (2 blister packs) to allow for unplanned delays in review visits.

Week T0

2 blister packs (14 days supply) of 0.5mg dispensed to family by the RP.

Week T+1

Prior to performing the home visit, 1 blister pack of 0.5mg along with 2 blister packs of 2mg (to provide a total of 14 days supply of each) will be dispensed to the Research Practitioner (RP). During the home visit the RP will evaluate the effectiveness of the treatment dose supplied at T0W in accordance with the dose modification criteria (section 7.9.1) and will either issue an additional blister pack of 0.5mg if this dose is to continue for a further week, or increase the dose and supply 2 blister packs of 2mg for the next week of treatment plus an additional pack.

All unused medication (including omitted doses from the previous week's regimen) will be collected by the RP and returned to pharmacy where they will be retained for destruction by PENN at study completion.

Week T+2

The RP will collect 1 week's supply of trial treatment at the patients current dose level, i.e. the same dose level as was prescribed at the T+1W home visit, in addition to 2 weeks supply of the next scheduled dose increase and 2 weeks supply of the previous dose (if applicable).

During the home visit the RP will evaluate the effectiveness of the treatment dose supplied at T+1W in accordance with the dose modification criteria (section 7.9.1) and will either issue an additional blister pack of the current dose level if this is to continue for a further week, or increase the dose, supplying 2 blister packs of the next dose increment, sufficient for the next week of treatment plus an additional pack. The dose may also be reduced (where applicable) due to the development of unacceptable adverse events or a change in the patient's condition (section 7.9.2). In this case the RP will supply 2 blister packs of the preceding dose.

All unused medication (including omitted doses from the previous week's regimen) will be collected by the RP and returned to pharmacy where they will be retained for destruction by PENN at study completion.

Week T+3

The RP will collect 1 week's supply of trial treatment at the patient's current dose level, i.e. the same dose level as was prescribed at the T+2W home visit, in addition to 2 week's supply of the next scheduled dose increase and 2 weeks supply of the previous dose (if applicable).

During the home visit the RP will evaluate the effectiveness of the treatment dose supplied at T+2W in accordance with the dose modification criteria (section 7.9.1) and will either issue an additional blister pack of the current dose level if this is to continue for a further week, or increase the dose, supplying 2 blister packs of the next dose increment, sufficient for the next week of treatment plus an additional pack. The dose may also be reduced (where applicable) due to the development of unacceptable adverse events or a change in the patient's condition (section 7.9.2). In this case the RP will supply 2 blister packs of the preceding dose.

All unused medication (including omitted doses from the previous week's regimen) will be collected by the RP and returned to pharmacy where they will be retained for destruction by PENN at study completion.

Week T+4

If the maximum daily dose (12mg) has been achieved at the T+3 home visit, the RP will collect sufficient 12mg capsules for the remaining 8 weeks of the trial treatment schedule from the pharmacy department. The RP will also collect 8 blister packs of 6mg capsules in case of a dose reduction.

If the dose level achieved by T+3W is 0.5mg then the RP will collect sufficient capsules to continue on the current dose i.e. the same dose level as was prescribed at the T+3W home visit, in addition to 8 weeks' supply of the next scheduled dose increase.

If the dose level is 2mg or 6mg at T+3W then the RP will collect sufficient capsules to continue on the current dose i.e. the same dose level as was prescribed at the T+3W home visit, in addition to 8 weeks' supply of the next scheduled dose increase and 8 week's supply of the lower dose in case of a dose reduction.

During the home visit the RP will evaluate the effectiveness of the treatment dose supplied at T+3W in accordance with the dose modification criteria (section 7.9.1) and will either issue 7 weeks' supply of the current dose level, if this is to continue for the duration of the study, or increase the dose, supplying 8 blister packs of the next dose increment, sufficient for the remaining 8 weeks of treatment. There is also the possibility of a dose reduction due to the development of unacceptable adverse events or a change in the patient's condition (section 7.9.2). In this case the RP will supply 8 blister packs of the preceding dose.

All unused medication (including omitted doses from the previous week's regimen) will be collected by the RP and returned to pharmacy. At pharmacy, unused medication from the previous week's regimen will be retained for destruction by PENN at study completion. Complete treatment packs taken by the RP to allow dose modifications at the study visit will be returned to pharmacy stores to be held on behalf of the patient, in case they need to be reissued to the patient at a subsequent visit.

Weeks T+5 and T+6

If the dose level prescribed at T+4W is 0.5mg, 2mg, or 6mg, and this is judged to be ineffective by the parent/carer in weeks T+5W or T+6W then an unscheduled visit should be arranged. A decision by the RP to increase the treatment dose may be made at this visit if the dose modification criteria (section 7.9.1) are met. If any of the dose modification criteria are not met, or if there is any doubt, the current dose should be maintained.

Sufficient capsules for the remaining trial period should be supplied and all unused medication at the lower dose level (including omitted doses from the previous week's regimen) should be collected by the RP and returned to pharmacy. At pharmacy, unused medication from the previous week's regimen will be retained for destruction by PENN at study completion. Complete treatment packs will be returned to pharmacy stores to be held on behalf of the patient, in case they need to be reissued to the patient at a subsequent visit. Dose reductions are permitted at T+5 to T+6 if required (section 7.9.2). If a dose reduction is required an unscheduled visit will be arranged to provide sufficient capsules of the preceding dose for the remainder of the trial period. At pharmacy, unused medication from the previous week's regimen will be retained for destruction by PENN at study completion. Complete treatment packs will be returned to pharmacy stores to be held on behalf of the patient, in case they need to be reissued to the patient at a subsequent visit.

Weeks T+7 to T+11

No dose increases are permitted for the remainder of the trial period. Dose reductions are permitted from T+7 to T+11 if required (section 7.9.2). If a dose reduction is required an unscheduled visit will be arranged to provide sufficient capsules of the preceding dose for the remainder of the trial period. At pharmacy, unused medication from the previous regimen will be retained for destruction by PENN at study completion.

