7.6 Accountability Procedures for Study Treatment/s

Throughout the study, patients will always be provided with a 7 day excess of their current treatment dose to allow for any unexpected delay in home or clinic visits. At randomisation (T0) the RP will collect 2 blister packs (7x0.5mg capsules in each) from pharmacy from the next patient pack to be assigned. The dispensing pharmacist will put the blister packs into a blank carton and put their local dispensing sticker (including patient name, patient address, pharmacy address and date) on to the carton, and will complete, sign and date the accountability log. The RP will also sign and date the accountability log. The RP will record the randomisation number on the pack in the eCRF. At each subsequent visit the RP will be provided with 1 blister pack (7 capsules) of the current dose, 2 blister packs of the next higher dose (if applicable) and 2 blister packs of the lower dose (if applicable, in case of dose reduction). The RP will ask the parents/guardians whether any doses have been missed during the preceding week and will check that this information corresponds with the number of capsules remaining in the blister pack. At each visit any extra medication and any used packages will be returned to the site pharmacy by the RP and will be signed for by the pharmacist who will record the number of capsules returned (See drug accountability log in Appendix I). At the end of the trial all medication will be returned to PENN for central destruction.

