Appendix I: Drug Accountability Log

MENDS Treatment Accountability Log
Version 2.1 031207

Centre Number: ____
Registration Number _____

Randomisation Number _____ assigned by _____ checked by _____
Sign and date Sign and date

Batch Number _____

For each visit, please complete the quantity of capsules dispensed and the quantity of capsules returned.

Visit	Strength	0.5mg	2 mg	6 mg	12 mg	Current Dose	Pharmacy Signature	Date dd/mm/yyyy	RP Signature	Date dd/mm/yyyy
T0W	Quantity of capsules issued	14								
	Quantity of capsules returned	0				0.5 mg				
T+1W	Quantity of capsules issued	7	14							
	Quantity of capsules returned									
T+2W	Quantity of capsules issued									
	Quantity of capsules returned									
T+3W	Quantity of capsules issued									
	Quantity of capsules returned									
T+4W	Quantity of capsules issued									
	Quantity of capsules returned									
T+5W	Quantity of capsules issued									
	Quantity of capsules returned									
T+6W	Quantity of capsules issued									
	Quantity of capsules returned									

At T0, 14 x 0.5mg capsules will be issued.

At T+1, 7 x 0.5mg capsules and 14 x 2mg capsules will be issued to allow for a dose increase.

At T+2, 7 capsules of the current dose and 14 capsules of both the lower and higher doses (if applicable) will be issued.

At T+3, 7 capsules of the current dose and 14 capsules of both the lower and higher doses (if applicable) will be issued.

At T+4, 49 capsules of the current dose, and 56 capsules of both the lower and higher doses (if applicable) will be issued.

At the T+5 telephone call an unscheduled visit can be arranged to increase or reduce the dose, therefore 49 capsules of the lower and/or higher dose as applicable will be issued for the remainder of the study.

At the T+6 telephone call an unscheduled visit can be arranged to increase or reduce the dose, therefore 42 capsules of the lower and/or higher dose will be issued as applicable for the remainder of the study.

Unscheduled visits (T+7W to T+12W) for dose reductions only

Visit	Strength	0.5mg	2 mg	6 mg	12 mg	Current Dose	Pharmacy Signature	Date dd/mm/yyyy	RP Signature	Date dd/mm/yyyy
	Quantity of capsules issued									
	Quantity of capsules returned									
	Quantity of capsules issued									
	Quantity of capsules returned									
	Quantity of capsules issued									
	Quantity of capsules returned									
	Quantity of capsules issued									
	Quantity of capsules returned									

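### The drug-collection wording conflicts with the T+4W issue quantity: applied literally, it leaves a child on an unchanged dose 5 to 7 capsules short in the final, primary-outcome week

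*Protocol*

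**What the plan says.** **Issue.** Protocol Section 7.4.1 gives each child a pack of 12 blisters of 0.5 mg, 11 of 2 mg, 10 of 6 mg and 9 of 12 mg, seven capsules to a blister. Two blisters are issued when a strength is started, and one more at each weekly visit before T+4W if it continues. At T+4W the practitioner is to "issue 7 weeks' supply of the current dose level, if this is to continue for the duration of the study". A child whose dose is raised at that visit instead receives eight blisters, described as "sufficient for the remaining 8 weeks of treatment". Appendix I agrees: "At T+4, 49 capsules of the current dose, and 56 capsules of both the lower and higher doses (if applicable) will be issued".

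**Collection.** For T+1W to T+4W, Section 7.4.1 says: "All unused medication (including omitted doses from the previous week's regimen) will be collected by the RP and returned to pharmacy". Section 7.6 adds: "At each visit any extra medication and any used packages will be returned to the site pharmacy by the RP". The one exception written at T+4W covers complete packs that the practitioner brought along in case of a dose change. It does not mention the family's own spare blister.

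**Text that points the other way.** Section 7.4.1 at T+1W counts one further 0.5 mg blister as bringing the supply to 14 days, which is true only if the first spare is still there. Section 7.7 limits collection at the weekly home visits to what is left from the preceding week. Section 8.2 at T+11W lets the family keep enough for the last week. Section 7.6 also states: "Throughout the study, patients will always be provided with a 7 day excess of their current treatment dose".

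**Outcome week.** Section 9.3.1 compares diary week T+11W with week T-1W. Sections 8.2 and 8.3.2 place the only on-treatment actigraphy in the final week.

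**The concern.** Seven weeks of capsules are issued for eight weeks of treatment. The missing week must come from the spare blister already in the home, yet two sections tell the practitioner to take unused or extra medication away and neither exempts that spare. A site that follows the collection sentences as written removes the capsules that the issue quantity relies on.

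The shortfall would come at the end of the supply, between T+11W and T+12W, where the primary diary comparison and the on-treatment actigraphy are made. Untreated nights there would be expected to pull the melatonin-placebo difference towards zero. Contacts from T+5W to T+10W are telephone calls, so no scheduled visit before T+11W would count the capsules.

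**Working it through.** **Inputs.** One capsule per night (7.4.2). Blister of 7, pack contents 12/11/10/9, and the issue rules above (7.4.1). T+4W issue of 49 capsules if the dose is unchanged and 56 if it changes; 49 at T+5W and 42 at T+6W after a later change (Appendix I). Two doses deliberately omitted at T+10W (8.6.3.1).

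**1. Reproduce the pack contents, with the spare kept at home.** Blisters issued to a child who reaches a strength at the earliest visit and stays on it:

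| Strength | Earliest visit | Blisters issued to T+12W | In pack |
|---|---|---|---|
| 0.5 mg | T0 | 2+1+1+1+7 = 12 | 12 |
| 2 mg | T+1W | 2+1+1+7 = 11 | 11 |
| 6 mg | T+2W | 2+1+7 = 10 | 10 |
| 12 mg | T+3W | 2+7 = 9 | 9 |

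All four agree. At T+4W the home holds 7 + 49 = 56 capsules for 8 × 7 = 56 nights, so no night is uncovered and nothing is left over.

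**2. Apply the collection sentences literally.** Of the first 14 capsules of a strength, 7 are used and 7 are taken back at the next visit. Each later single blister is then used up within its week. At T+4W the home holds 0 + 49 = 49 capsules.

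- Shortfall: 56 − 49 = 7 capsules. Supply ends at T+11W.
- If the two capsules omitted at T+10W remain with the family: 7 − 2 = 5.
- If they are collected at T+11W, as 7.7 reads: 7.

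With otherwise full adherence the gap is therefore 5 to 7 nights of the last week, whichever strength the child is on. A child whose dose is raised or lowered at T+4W receives 56 capsules for 56 nights and has no gap.

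**3. Could the pharmacy issue eight blisters instead?** With literal collection and eight blisters at T+4W, the earliest-visit paths need 13, 12, 11 and 10 blisters against 12, 11, 10 and 9 supplied. Each is one short. A child who reaches a strength later may have a blister in reserve: reaching 6 mg at T+3W uses 2 + 7 = 9 of 10.

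**4. Check the 7-day excess from T+4W.**

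| Situation | Capsules | Nights left | Excess |
|---|---|---|---|
| Unchanged at T+4W, spare kept | 56 | 56 | 0 |
| Changed at T+4W | 56 | 56 | 0 |
| Changed at T+5W | 49 | 49 | 0 |
| Changed at T+6W | 42 | 42 | 0 |

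The T+10W omissions can leave two capsules, not seven.

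**5. Check the 6 mg reduction stock.** For a child already on 12 mg, Section 7.4.1 at T+4W says: "The RP will also collect 8 blister packs of 6mg capsules in case of a dose reduction". If the dose was raised at every visit, 10 − 2 = 8 blisters remain, which meets the requirement.

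**The case against.** The strongest reply is that the quantities are right and the intention is clear. The four totals in step 1 match the pack contents exactly. The amendment history in Section 18 shows that 7 weeks at T+4W was chosen deliberately in place of 8. The 14-day count at T+1W, the narrower collection rule in 7.7 and the T+11W text in 8.2 all assume that the spare stays. A site that took it back would itself breach those passages. This stands: the number 7 is not an error, and the defect is confined to the collection wording. It does not remove the conflict, because 7.4.1 and 7.6 still give the opposite instruction without an exception.

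Two stronger readings are tempting and should not be drawn.

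- **That melatonin children will be untreated in the outcome week and the result biased.** The gap depends on literal collection and concerns only children unchanged at T+4W. The T+11W home visit includes a pill count (7.7) and opens the final week, so it could reveal a shortage. Nothing in the documents shows how sites read the wording or how large any dilution would be.
- **That the 6 mg reduction stock is also short (10 − 2 − 1 = 7 against 8).** This assumes that a blister carried to T+3W but not issued is destroyed. The T+1W to T+3W text does not say so; it reads most naturally as medication taken back from the family.

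It may also be said that the 7-day excess was meant only for the dose-increasing phase, where 7.4.1 explains it as cover for delayed visits. That is plausible, but 7.6 states it for the whole study.

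**Conclusion.** The concern holds as a conflict of wording, not as a wrong quantity. The T+4W issue of 49 capsules covers 56 nights only if the spare blister stays at home, and the collection sentences in 7.4.1 and 7.6 do not let it stay. Followed literally, they leave a child with an unchanged dose 5 to 7 capsules short between T+11W and T+12W. A child who reached the strength at the earliest visit would have no unissued blister of it left to make this good. Separately, the 7-day excess claimed for the whole study is zero from T+4W even on the most favourable reading.

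This rests on one capsule per night, no missed doses other than the two planned ones, and week T+11W being the week that starts at the T+11W visit. That last point follows from 8.2 and from 8.6.3.1, which treats T+10W as the start of the eleventh week. Section 7.7, however, labels the last week's blister T+12W, so the week labels need aligning too. The size of any effect on the treatment difference cannot be derived from the documents.

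**What to change.** Reconcile 7.4.1, 7.6, 7.7, the T+11W entry in 8.2 and Appendix I:

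- State that at T+1W to T+4W the unopened spare blister of a continuing dose is counted but left with the family, and that only leftover capsules from the previous week or from a discontinued strength are collected.
- Limit the 7-day-excess sentence in 7.6 to the period before T+4W.
- Use one label for the last treatment week in 7.7, 8.2 and 9.3.1.
- As a clarification only, say that packs carried but not issued at T+1W to T+3W go back to the patient's stock, as is already said for T+4W.

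The cost is a few sentences, a matching line in the accountability log, and a note to pharmacies and research practitioners. No extra drug is needed if the spare stays at home, and no dose rule changes. Issuing eight blisters at T+4W while still collecting the spare is not an equivalent remedy, because on the earliest-visit paths it needs one more blister of each strength than the packs contain.
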